22.0 Withdrawal of Subjects*

- N/A:** This study is not enrolling subjects. This section does not apply.

22.1 Describe anticipated circumstances under which subjects may be withdrawn from the research without their consent.

Response:

Subjects who do not adhere to the protocol procedures and study instructions may be withdrawn from research analyses, as determined by the Principal Investigator and/or NIH Data Safety Committee. In addition to not adhering to study instructions, possible reasons for removal include nonsystematic responding to questionnaires. If a participant is withdrawn from the study without their consent, they will be debriefed about the nature of the study and be compensated for the amount of time spent in the study. We may also stop an ongoing session, or end participation in the study because we have collected all the information we need.

22.2 Describe any procedures for orderly termination.

NOTE: Examples may include return of study drug, exit interview with clinician. Include whether additional follow up is recommended for safety reasons for physical or emotional health.

Response:

Participants will be debriefed about the nature of the study and the reason for their removal. No additional follow-up is needed.

22.3 Describe procedures that will be followed when subjects withdraw from the research, including retention of already collected data, and partial withdrawal from procedures with continued data collection, as applicable.

Response:

Participants can withdraw from the research at any time. If participants withdraw, no further data will be collected, but any information that had been provided may be retained by the researcher and analyzed.

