We propose an RCT that will assess the effects of EFT on medication adherence, general PM, and DD among those with pre- or type 2 diabetes or related comorbidities who are currently taking at least one oral medication for diabetes or related comorbidities. We will recruit participants who are relatively non-adherent to an oral medication ($\leq 80\%$ of prescribed doses taken in the past month; to accommodate over-reporting) for prediabetes or type 2 diabetes or other conditions that commonly co-occur with these conditions (e.g., hypertension, hyperlipidemia). Medication adherence will be monitored using electronic pill bottle caps (MEMS caps, which record bottle openings with date and time stamps), pill counts, and pharmacy records. Medications for glucose control as well as control of hypertension and/or hyperlipidemia will be considered as targets for measurement. Participants self-rated as non-adherent ($\leq 80\%$ prescribed doses taken), and report difficulty remembering to take one’s medication as a primary reason for non-adherence, will undergo a 6 week, 8 week, or 10 week baseline period. After the staggered baseline periods, all participants will receive EFT intervention. In total, participants will be in baseline and treatment for a total of 15 weeks.

Randomized participants will complete bi-weekly in person sessions plus phone sessions for the weeks in which they do not come to the lab, in which they learn to engage in EFT for medication adherence. Initial EFT for medication adherence will focus on taking the targeted medication on a typical day (e.g., a weekday when the participant usually works), and in subsequent sessions EFT will be used to assist participants in adapting to unusual circumstances that may interrupt adherence or have been reported as contributing to non-adherence.

At an initial baseline session, post-intervention, and follow-up, participants will complete measures of working memory, lab-based PM, and DD. Dependent measures include change in targeted medication adherence (based on MEMS data), change in non-targeted medication adherence (for participants initially reporting non-adherence to multiple medications; based on self-report and pill count measures), DD, and PM. Moderators to be tested include working. The goal of the study will be to collect pilot data to test the feasibility and initial efficacy of the approach, as well as effect sizes for a subsequent R01.

4.2 Include complete citations or references.

Response:

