7.0 36 Local Number of Subjects

7.1 Indicate the total number of subjects that will be enrolled or records that will be reviewed locally.

Response:

Up to 20 subjects will be enrolled from Buffalo, and the neighboring cities. Subjects will be randomized after completion of the baseline period. The goal will be to randomize at least 10-12 participants.

7.2 If applicable, indicate how many subjects you expect to screen to reach your target sample (i.e. your screen failure rate).

Response:

We expect to initially screen approximately 60 subjects (online or by phone screen survey) and complete about 20 in person and baseline screenings.

7.3 Justify the feasibility of recruiting the proposed number of eligible subjects within the anticipated recruitment period. For example, how many potential subjects do you have access to? What percentage of those potential subjects do you need to recruit?

Response:

Given that we will be taking advantage of CTSI resources for recruiting based on individuals' diagnosed medical conditions, we anticipate that recruiting this relatively small number of participants for our final sample will be feasible within a 4-month period. The Buffalo Research Registry has 200-some potentially eligible individuals based on a diagnosis of Pre- or Type 2 Diabetes, and TriNetX an additional 15,110 with these diagnoses (with 5,150 of these prescribed an oral blood glucose-regulating medication).

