Participants assigned to IC will be asked to generate cues about newly-learned health information. For this activity, the research staff will provide participants with a weekly learning module that will consist of presenting information on relevant health-related topics (e.g., information about diagnosed conditions that made them eligible for participation), which may include brief quizzes, informational videos, and other learning-oriented activities that may help with information retention (e.g., playing a memory game incorporating information about glucose metabolism). Participants will be asked to generate cues about the course content which may include imagining different ways the information could be useful, how it could be applied in different contexts, with different people, etc. As in EFT, participants will be asked open-ended questions as needed to prompt more details, and IC participants may also audio record their cues.

Participants will be asked to rate their cues on different dimensions (e.g., vividness, usefulness, valence, salience), which will be used to calculate a richness score (average of dimension ratings).

EFT participants may be provided the same information that IC participants are provided, to ensure both groups are equally knowledgeable on the topics; this information may be provided in a different format for ease of use/reference outside of the laboratory (e.g., on a study website, pamphlet, or booklet).

Participants will be trained to use EFT/IC outside of the lab using the ecological momentary intervention (EMI) computer based program that we have developed: the Mobile Audio Management and Response Tracker (MAMRT). This program, which is part of the study website, can be accessed by smartphone, tablet or computer. This application stores participants' EFT/IC cues, prompts their use (e.g., reminder text message, reminder email), asks questions about use of their cues, and records their use. Participants will be instructed to practice using EFT/IC daily. The MAMRT software was previously approved in STUDY00000936, and appears in Sze, Daniel, Kilanowski, Collins, and Epstein, 2015. In addition to the above, the MAMRT website may also be used to provide health information (i.e., that provided to the IC group), and other activities such as

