19.0 Data Management and Analysis*

19.1 Describe the data analysis plan, including any statistical procedures. This section applies to both quantitative and qualitative analysis.

Response:

Pill count and MEMS data displayed as a percentage of doses taken will be displayed graphically to enable visual analysis of changes in means and trends of dependent variables across the different phases of the study.

Borckardt, J., & Nash, M. (2014). Simulation modelling analysis for small sets of single-subject data collected over time. *Neuropsychological Rehabilitation*, 24(3-4), 492–506. <https://doi.org/10.1080/09602011.2014.895390>

19.2 If applicable, provide a power analysis.

NOTE: This may not apply to certain types of studies, including chart/records reviews, survey studies, or observational studies. This question is asked to elicit whether the investigator has an adequate sample size to achieve the study objectives and justify a conclusion.

Response:

A power analysis is not applicable to this multiple baseline design. We are collecting weekly data from participants and will have enough data points to ensure we will be able to achieve the study objectives. The results of this study will be analyzed graphically as well as assessing the degree of change from baseline to treatment across the three replications. For an example of a study that utilized a multiple baseline design, see:

19.3 Describe any procedures that will be used for quality control of collected data.

Response:

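### Section 22.1 lets participants be dropped from the analyses at discretion for not following instructions, and section 19 defines no analysis set that limits this

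*Combined protocol and SAP*

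**What the plan says.** Section 22.1 answers a question about withdrawing subjects without their consent. Its first sentence goes further and reaches the analyses: participants who fail to follow "protocol procedures and study instructions may be withdrawn from research analyses, as determined by the Principal Investigator and/or NIH Data Safety Committee". It then adds: "In addition to not adhering to study instructions, possible reasons for removal include nonsystematic responding to questionnaires". No number of missed sessions, scoring rule, decision time or reporting duty follows.

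The instructions in question include use of the intervention itself. Section 12.1 states: "Participants will be instructed to practice using EFT/IC daily". No minimum amount of practice is set.

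On the analysis, section 19.1 states: "Pill count and MEMS data displayed as a percentage of doses taken will be displayed graphically to enable visual analysis". Section 19.2 adds that the results will be examined by "assessing the degree of change from baseline to treatment across the three replications". Neither says which participants are included. Section 19.3 covers data integrity and ID coding.

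On size and purpose, section 7.1 states: "The goal will be to randomize at least 10-12 participants". Section 4.1 says that the pilot is to provide feasibility and initial efficacy data, "as well as effect sizes for a subsequent R01".

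**The concern.** Adherence behaviour is the primary outcome, and failure to follow instructions is a ground for removal. These are different things, but it is plausible that they are related. Someone who practises little may also change little.

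The person who may decide on removal is not kept from the data. Under sections 21.1, 21.2 and 21.5, study measurements are reviewed and the investigator takes part in a weekly review. Nothing requires the decision to be made without sight of adherence.

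Each participant serves as their own control, so dropping one leaves the other displayed series unchanged. What can move is the summary across participants: the average change and the proportion who improve. Those are the quantities that a later grant application would use. Visual analysis gives no protection, because a series that has been removed is not on the page.

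**Working it through.** **Step 1: does anything limit 22.1?** The places that might do so are these.

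- Section 19 (19.1 to 19.3): no analysis set, exclusion rule or missing-data rule.
- Sections 8.1 and 12.1: numeric rules exist (80% adherence, and no increasing trend over 3 data points), but they govern eligibility and entry to the intervention. They do not govern later exclusion from the analysis.
- Section 22.3: when participants withdraw by choice, "any information that had been provided may be retained by the researcher and analyzed". This is as permissive as 22.1 and does not constrain it.

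So nothing limits it.

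**Step 2: how large could the effect be?** The plan gives no figure to reproduce: no test, alpha, SD, expected effect or number of removals, and no correlation between engagement and response. What follows shows direction and possible size only.

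Inputs:
- N = 12 or 10 participants starting the intervention (from the randomisation goal in 7.1, assuming that all start).
- k = 1 or 2 least engaged participants removed (assumed).
- r = correlation between engagement and change in adherence: 0, 0.3 or 0.5 (assumed).
- Change in SD units, normally distributed (assumed).

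Shift in the kept mean = r × (minus the sum of the k lowest expected normal order statistics) / (N − k).

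- N = 12: the two lowest are −1.629 and −1.116. The multiplier is 1.629/11 = 0.148 for k = 1 and 2.745/10 = 0.274 for k = 2.
- N = 10: the two lowest are −1.539 and −1.001. The multiplier is 1.539/9 = 0.171 for k = 1 and 2.540/8 = 0.318 for k = 2.

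| N | removed | r = 0 | r = 0.3 | r = 0.5 |
|---|---|---|---|---|
| 12 | 1 | 0 | +0.04 SD | +0.07 SD |
| 12 | 2 | 0 | +0.08 SD | +0.14 SD |
| 10 | 1 | 0 | +0.05 SD | +0.09 SD |
| 10 | 2 | 0 | +0.10 SD | +0.16 SD |

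**Step 3: share of kept participants who improve, with no true effect** (N = 12, by simulation with at least one million samples per setting; no hypothesis test is needed).

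| removed | r = 0 | r = 0.3 | r = 0.5 |
|---|---|---|---|
| 1 | 50% | 51.7% | 52.8% |
| 2 | 50% | 53.3% | 55.5% |

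**Step 4: two further illustrations that rest on analyses the plan does not contain.** Both use N = 12, two removed, and r = 0.3 to 0.5.

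- On an assumed one-sided 2.5% t-test of mean change, the false-benefit rate would be about 4.4% to 6.4%.
- If the true effect were 0.5 SD (assumed), a later trial sized on the inflated mean would have (0.5/(0.5 + shift))² of the needed sample. This is (0.5/0.582)² = 0.74 to (0.5/0.637)² = 0.62, so 26% to 38% too small.

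**The case against.** The best case for the plan is that 22.1 is loosely worded. It answers a template question about ending participation, and it moves from the analyses to removal and then to withdrawal from the study. It may mean no more than stopping someone's participation. That ambiguity is real, but the sentence as written names the analyses and nothing corrects it.

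The plan also has partial safeguards. A committee may share the decision, and under 22.2 the participant is told why they were removed. But the and/or wording lets the investigator decide alone, and telling the participant is not the same as reporting the exclusion with the results. Section 12.1 plans walk-through calls to support cue use, and no document says that removals are expected. With one removal at r = 0.3 the shift is 0.04 SD, which is negligible for a pilot.

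A reader might infer more than the documents support in three places:

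- *That removals would break the replication argument.* Section 19.2 speaks of three replications, most naturally the three baseline groups. With 10 to 12 randomised and even allocation there are about 3 to 4 per group, so losing one or two would not normally remove a group. No claim about the number of replications is made here.
- *That the plan treats voluntary withdrawals more protectively.* Section 22.3 is equally discretionary, so the contrast carries little weight.
- *That poor questionnaire answers will cost a participant their adherence series.* The text neither says so nor rules it out.

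**Conclusion.** The point holds and should be fixed. Section 22.1 gives an undefined discretion to drop participants from the analyses after randomisation, and nothing in section 19 or elsewhere limits it. Confidence in that textual finding is high.

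The size is much less certain. If removal is unrelated to change, there is no bias. If the two least engaged of 12 starters were removed and engagement correlated 0.3 to 0.5 with change, the mean would rise by 0.08 to 0.14 SD and, with no true effect, the share improving by 3.3 to 5.5 percentage points. The correlation and the number removed are assumptions.

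A reader might take the false-benefit and sample-size figures as properties of this trial. They are not, because no pooled test or R01 calculation is planned. Nor do the documents show that biased removal has happened or is intended. The text says only that participants may be removed, and the ground is not following instructions, not missing doses. The finding is that the plan leaves the route open.

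**What to change.** In 22.1, replace withdrawal from the analyses with withdrawal from study procedures only. In 22.1 and 19.1, add text along these lines:

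> Every randomised participant who starts the intervention is displayed and included in the primary analysis with all valid adherence data collected, whatever their engagement with EFT. The phase change is placed at the actual start of intervention. Randomised participants who never start are reported separately, with reasons and baseline data. Data are excluded only by criteria fixed before the data are examined (for example, nonsystematic discounting responses, or periods when the MEMS bottle was documented as not in use, for which pill counts are used). These criteria are applied mechanically, only to the affected measure, and results are shown with and without the exclusion.

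The clause on bottle use is needed because a participant who does not use the bottle produces missing openings that reflect measurement failure, not missed doses. The sentence on non-starters fits section 12.1, under which a randomised participant whose baseline is not stable moves to a later group and might never reach the intervention.

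The cost is about one paragraph and a short list of criteria, with no added visits, measurements or participants. Because the criteria are fixed and applied mechanically, no extra blinded decision-maker is needed despite the weekly data review. The downside is that the estimated effect may be smaller and the graphs more variable.

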23.0 Risks to Subjects*

23.1 List the reasonably foreseeable risks, discomforts, hazards, or inconveniences to the subjects related to their participation in the research. Consider physical, psychological, social, legal, and economic risks. Include a description of the probability, magnitude, duration, and reversibility of the risks.

NOTE: Breach of confidentiality is always a risk for identifiable subject data.

Response:

There may be some sensitivity associated from certain questions asked when filling out questionnaires or having body measurements taken and subjects might feel uncomfortable disclosing some personal information such as medical history. Subjects can refuse to answer any questions that they are not comfortable answering. Subjects will be free to withdraw from the study at any time, and their refusal to continue will not affect other medical care provided at any healthcare facility.

Breach of confidentiality is another potential risk. To protect confidentiality, we will use only ID numbers and keep all data in locked cabinets or in locked offices and password protected electronic files in password protected computers.

There are no other risks anticipated. All personnel on the study will be CITI course certified and have completed the good research practices certification. All identifiable data will be password protected and only the research team will have access to that information. Subjects will be informed of the risks associated with the study.

23.2 Describe procedures performed to lessen the probability or magnitude of risks, including procedures being performed to monitor subjects for safety.

Response:

We have several provisions in place to ensure participants' privacy and safety is protected while the data is being collected. The lab facilities of the Division of Behavioral Medicine research laboratory consist of private interview rooms that will be used. Only the relevant research staff and participant will be present in the room during sessions. Data is recorded such that not even the person putting it in the file would ever be able to associate the data with the identity of the person providing it. Data and files that have been de-identified and encrypted will be shared between sites. Therefore, there is no reasonable risk of a breach of confidentiality.

Should an emergency situation occur, access to further medical care is available via a telephone located in the laboratory and the following emergency plan will be followed:

1. Have the subject immediately stop any activity and lay down.
2. Call for help! ON CAMPUS EMERGENCY [contact]) or POLICE (911).
3. If the subject is unconscious – assess breathing and heart rate. Initiate CPR (if trained) and call on campus emergency services or police as necessary.
4. If the subject is conscious – continue to observe subject.

23.3 If applicable, indicate which procedures may have risks to the subjects that are currently unforeseeable.

Response:

N/A, subjects will be allowed to refuse to answer any questions they are not comfortable with.

23.4 If applicable, indicate which research procedures may have risks to an embryo or fetus should the subject be or become pregnant.

Response:

N/A, we will not be enrolling pregnant participants.

23.5 If applicable, describe risks to others who are not subjects.

Response:

N/A, no foreseeable risks to others who are not subjects.

24.0 Potential Benefits to Subjects*

24.1 Describe the potential benefits that individual subjects may experience by taking part in the research. Include the probability, magnitude, and duration of the potential benefits. Indicate if there is no direct benefit.

NOTE: Compensation cannot be stated as a benefit.

Response:

Participants may benefit from improved health due to better adherence to their prescribed medication(s). Participants may also learn about the experimental research process and their health.

25.0 Compensation for Research-Related Injury

N/A: The research procedures for this study do not present risk of research related injury (e.g. survey studies, records review studies). This section does not apply.

26.0 Economic Burden to Subjects

26.1 *Describe any costs that subjects may be responsible for because of participation in the research.*

NOTE: Some examples include transportation or parking.

Response:

Participants will be responsible for transportation to/from the laboratory for their scheduled sessions. If participants do not have their own personal mode of transportation, they may be reimbursed in the amount of standard bus/train fare. Participants will not incur parking fees at our laboratory.

N/A: This study is not enrolling subjects, or is limited to records review procedures only. This section does not apply.

27.0 Compensation for Participation

27.1 *Describe the amount and timing of any compensation to subjects, including monetary, course credit, or gift card compensation.*

Response:

Participants will receive \$35 for completion of each assessment session ($\$35 \times 3 = \105), and will receive additional compensation bonuses if they (a) complete all three assessment sessions (\$25), and (b) return the MEMS cap (\$20). The total possible compensation for participation in the study is \$150.

